9.3. Treatment of Missing and Spurious Data

See general definitions in chapter 5.4.

9.4. Exclusion of Particular Information

See general definitions in chapter 5.5.

9.5. Descriptive Analyses

See general definitions in chapter 5.1.

9.6. Hypotheses & Statistical Tests

There are no pre-defined statistical hypotheses.

¹¹ IF CMBLFL = Yes AND any CMCLAS = ACE inhibitors

¹² IF CMBLFL = Yes AND any CMCLAS = Angiotensin receptor ...

¹³ IF CMBLFL = Yes AND any CMCLAS = Aldosterone blocker

¹⁴ IF CMBLFL = Yes AND any CMCLAS = Betablocker ...

¹⁵ IF CMBLFL = Yes AND any CMCLAS = Calcium channel blocker

¹⁶ IF CMBLFL = Yes AND any CMCLAS = Digoxin

¹⁷ IF CMBLFL = Yes AND any CMCLAS = Statins

¹⁸ IF CMBLFL = Yes AND any CMCLAS = Diuretics

¹⁹ IF CMBLFL = Yes AND any CMCLAS = Anticoagulation

²⁰ IF CMBLFL = Yes AND any CMCLAS = Antiplatelets

²¹ IF CMBLFL = Yes AND any CMCLAS = Antiarrhythmics

²² IF CMBLFL = Yes AND any CMCLAS = ACE inhibitors OR
any CMCLAS = Angiotensin receptor ...

THEN med01_SAR= Yes ELSE med01_SAR = No

THEN med02_SAR= Yes ELSE med02_SAR = No

THEN med03_SAR= Yes ELSE med03_SAR = No

THEN med04_SAR= Yes ELSE med04_SAR = No

THEN med05_SAR= Yes ELSE med05_SAR = No

THEN med06_SAR= Yes ELSE med06_SAR = No

THEN med07_SAR= Yes ELSE med07_SAR = No

THEN med08_SAR= Yes ELSE med08_SAR = No

THEN med09_SAR= Yes ELSE med09_SAR = No

THEN med10_SAR= Yes ELSE med10_SAR = No

THEN med11_SAR= Yes ELSE med11_SAR = No

THEN med01_02_SAR= Yes

ELSE med01_02_SAR = No

10. Implantation Data: Ilivia

10.1. Analysis set

All analyses are performed for the Ilivia analysis set²³.

10.2. Variables

Implantation / ICD/CRTD

Data file, identifier patient_display_id_full	Descriptive	Variable name	Variable label	Variable level	Nominal values
implantation_general_data	Yes	imp_category	Study implantation	nominal	De novo CRT-D / ICD implantation Upgrade from pacemaker [...] Upgrade from ICD [...] Exchange of ICD / CRT-D [...]
implantation_general_data	Yes	imp_site	Implantation site	nominal	left / right
implantation_general_data	Yes	imp_dev_type_other	Device type	nominal	Single chamber ICD Dual Chamber ICD CRT-D
implantation_general_data	Yes	imp_dev	Device model	nominal	Ilivia 7 [...]
implantation_general_data	Yes	imp_dev_type	Device type	nominal	VR-T [...]
implantation_general_data	Yes	imp_connector	Connector type for RV lead	nominal	DF-1 / DF4

Implantation / Leads

Data file, identifier patient_display_id_full	Descriptive	Variable name	Variable label	Variable level	Nominal values
implantation_general_data	No	imp_rv_model	RV lead model	Nominal	Plexa S [...]
data_SAR	Yes	imp_rv_model_SAR ²⁴	RV lead model	Nominal	Plexa Other

²³ analysis_set_Ilivia_SAR = Yes

²⁴ IF imp_rv_model = Plexa S OR Plexa SD OR Plexa DF-1 S OR Plexa DF-1 SD or Plexa DF-1 S DX
THEN imp_rv_model_SAR = Plexa
ELSE imp_rv_model_SAR = other

Implantation Analyzer Data / RA

Data file, identifier_patient_display_id_full	Descriptive	Variable name	Variable label NEW prefix added to all labels "Implantation analyzer data, RA: "	Variable level	Nominal values
implantation_analyzer_data	Yes	imp_ana_ra_amp	Sensing amplitude [mV]	scale	n.a.
implantation_analyzer_data	Yes	imp_ana_ra_imp	Pacing impedance [Ω]	scale	n.a.
implantation_analyzer_data	Yes	imp_ana_ra_thresh	Pacing threshold [V] at Pulse width 0.4 ms	scale	n.a.
implantation_analyzer_data	No	imp_ana_ra_thresh2	Pacing threshold [V]	scale	n.a.
implantation_analyzer_data	No	imp_ana_ra_pulse	at Pulse width [ms]	scale	n.a.
data_SAR	Yes	imp_ana_ra_thresh_0 ⁵ ₂₅	Pacing threshold [V] at Pulse width 0.5 ms	scale	n.a.

A pacing threshold must always consist of amplitude and duration (pulse width). It is not reasonable to report one without the other.

Here, the CIP requires using 0.4 ms, but it can be expected that other pulse durations were used because different analyzer devices which are being used in the investigational centers have different standard settings.

In the SAP version 1.0 it has been defined that it will be tested during blind review whether a meaningful number of measurements were performed with another pulse duration than 0.4 ms.

This test showed that, in fact, in a meaningful number of threshold measurements, 0.5 ms has been used, but only single or no other values. The same was found for other analyzer threshold measurements at the implantation (RV, LV).

Therefore, **thresholds of analyzer measurements will be reported for 0.4 and 0.5 ms pulse duration**. Measurements at other pulse duration (if any) will be discarded.

²⁵ IF imp_ana_ra_pulse =0.5 THEN imp_ana_ra_thresh_05 = imp_ana_ra_thresh2

Implantation Analyzer Data / RA / Not-measured

Data file, identifier patient_ display_id_full	Descriptive	Variable name	Variable label	Variable level	Nominal values
implantation_analyzer_data	No	imp_ana_ra_amp_no	-	nominal	Not measurable: P-wave visible but [...] Not measurable: No P-wave visible Not done
data_SAR	Yes	imp_ana_ra_amp_no_SAR ²⁶	Implantation analyzer data, RA: Sensing amplitude	nominal	Not measurable: P-wave visible but [...] Measured
implantation_analyzer_data	No	imp_ana_ra_imp_no	-	nominal	Above range Below range Not measurable: no overdrive pacing Not done
data_SAR	Yes	imp_ana_ra_imp_no_SAR ²⁷	Implantation analyzer data, RA: Pacing impedance	nominal	Out of range Measured
implantation_analyzer_data	No	imp_ana_ra_thresh_no	-	nominal	Not measured at 0.4 ms No capture with maximum output [...] Not measurable: no overpacing possible Not done
data_SAR	Yes	imp_ana_ra_thresh_no_SAR ²⁸	Implantation analyzer data, RA: Pacing threshold	nominal	No capture with maximum output [...] Measured

²⁶ IF imp_ana_ra_amp_no = Not measurable: P-wave visible but ...
THEN imp_ana_ra_amp_no_SAR = imp_ana_ra_amp_no
ELSE IF imp_ana_ra_amp ≠ missing
THEN imp_ana_ra_amp_no_SAR = Measured

²⁷ IF imp_ana_ra_imp_no = Above range OR imp_ana_ra_imp_no = Below range
THEN imp_ana_ra_imp_no_SAR = Out of range
ELSE IF imp_ana_ra_imp ≠ missing THEN imp_ana_ra_imp_no_SAR = Measured

²⁸ IF imp_ana_ra_thresh_no = No capture ... THEN imp_ana_ra_thresh_no_SAR = imp_ana_ra_thresh_no
ELSE IF imp_ana_ra_thresh ≠ missing THEN imp_ana_ra_thresh_no_SAR = Measured

All rights pertaining to this document are exclusively held by BIOTRONIK SE & Co. KG. Any non-authorized copying, reproduction or distribution is not permitted. Confidentiality: This document and/or its contents are only for internal use.

Implantation Analyzer Data / RV

Data file, identifier patient_display_id_full	Descriptive	Variable name	Variable label NEW prefix added to all labels "Implantation analyzer data, RV: "	Variable level	Nominal values
implantation_analyzer_data	Yes	imp_ana_rv_amp	Sensing amplitude [mV]	scale	n.a.
implantation_analyzer_data	Yes	imp_ana_rv_imp	Pacing impedance [Ω]	scale	n.a.
implantation_analyzer_data	Yes	imp_ana_rv_thresh	Pacing threshold [V] at Pulse width 0.4 ms	scale	n.a.
implantation_analyzer_data	No	imp_ana_rv_thresh2	Pacing threshold [V]	scale	n.a.
implantation_analyzer_data	No	imp_ana_rv_pulse	at Pulse width [ms]	scale	n.a.
data_SAR	Yes	imp_ana_rv_thresh0 ²⁹	Pacing threshold [V] at Pulse width 0.5 ms	scale	n.a.

Pacing threshold measurements will be reported for 0.4 and 0.5 ms separately. See the justification above.

Implantation Analyzer Data / RV / Not-measured

Data file, identifier patient_display_id_full	Descriptive	Variable name	Variable label	Variable level	Nominal values
implantation_analyzer_data	No	imp_ana_rv_amp_no	-	nominal	No intrinsic rhythm Amplitude visible but too low to measure During intrinsic rhythm no R-wave visible Not done
data_SAR	Yes	imp_ana_rv_amp_no_SAR ³⁰	Implantation analyzer data, RV: Sensing amplitude	nominal	Amplitude visible but too low to measure During intrinsic rhythm no R-wave visible Measured
implantation_analyzer_data	No	imp_ana_rv_imp_no	-	nominal	Above range Below range Not measurable: no overpacing possible Not done
data_SAR	Yes	imp_ana_rv_imp_no_SAR ³¹	Implantation analyzer data, RV: Pacing impedance	nominal	Out of range Measured
implantation_analyzer_data	No	imp_ana_rv_thresh_no	-	nominal	Not measured at 0.4 ms No capture with maximum output [...] Not measurable: no overpacing possible Not done
data_SAR	Yes	imp_ana_rv_thresh_no_SAR ³²	Implantation analyzer data, RV: Pacing threshold	nominal	No capture with maximum output [...] Measured

²⁹ IF imp_ana_rv_pulse =0.5 THEN imp_ana_rv_thresh_05 = imp_ana_rv_thresh2

³⁰ IF imp_ana_rv_amp_no = Amplitude visible ...OR
imp_ana_rv_amp_no = During intrinsic ... THEN imp_ana_rv_amp_no_SAR = imp_ana_rv_amp_no
ELSE IF imp_ana_rv_amp \neq missing THEN imp_ana_rv_amp_no_SAR = Measured

³¹ IF imp_ana_rv_imp_no = Above range OR Below range THEN imp_ana_rv_imp_no_SAR = Out of range
ELSE IF imp_ana_rv_imp \neq missing THEN imp_ana_rv_imp_no_SAR = Measured

Implantation Analyzer Data / LV / 7 Sensing Vectors

Data file, identifier_patient_display_id_full	Descriptive	Variable name	Variable label, NEW prefix added to all labels "Implantation analyzer data, [specification ... to ...]: "	Variable level	Nominal values
implantation_analyzer_data	Yes	imp_ana_lv_amp_01	Sensing amplitude [mV]	scale	n.a.

The above analyses are performed for all 7 vector permutations, respectively:

- 01 LV1 tip to LV2 ring
- 02 LV1 tip to ICD
- 03 LV2 ring to LV3 ring
- 04 LV2 ring to ICD
- 05 LV3 ring to LV4 ring
- 06 LV3 ring to ICD
- 07 LV4 ring to ICD

Implantation Analyzer Data / LV / 7 Sensing Vectors / Not-measured

Data file, identifier_patient_display_id_full	Descriptive	Variable name	Variable label	Variable level	Nominal values
implantation_analyzer_data	No	imp_ana_lv_svect_no	-	nominal	No intrinsic rhythm Amplitude visible but too low to measure During intrinsic rhythm no R-wave visible Not done
data_SAR	Yes	imp_ana_lv_svect_no_SAR ³³	Implantation analyzer data: Any LV pacing vector	nominal	Amplitude visible but too low to measure During intrinsic rhythm no R-wave visible At least one vector measured

³² IF imp_ana_rv_thresh_no = No capture ... THEN imp_ana_rv_thresh_no_SAR = imp_ana_rv_thresh_no
ELSE IF imp_ana_rv_thresh ≠ missing THEN imp_ana_rv_thresh_no_SAR = Measured

³³ IF imp_ana_lv_svect_no = Amplitude visible but too low to measure
THEN imp_ana_lv_svect_SAR = Amplitude visible but too low to measure
ELSE IF imp_ana_lv_amp_0j_no = During intrinsic rhythm no R-wave visible
THEN imp_ana_lv_svect_no = During intrinsic rhythm no R-wave visible
ELSE IF any j=1-7 imp_ana_lv_amp_0j ≠ missing
THEN imp_ana_lv_svect_SAR = At least one vector measured

Implantation Analyzer Data / LV / 12 Pacing Vectors

Data file, identifier_patient_display_id_full	Descriptive	Variable name	Variable label, NEW prefix added to all labels "Implantation analyzer data, [specification ... to ...]: "	Variable level	Nominal values
implantation_analyzer_data	Yes	imp_ana_lv_imp_01	Pacing impedance [Ω]	scale	n.a.
implantation_analyzer_data	No	imp_ana_lv_thresh_01	Pacing threshold [V]	scale	n.a.
implantation_analyzer_data	No	imp_ana_lv_pulse_01	at Pulse width [ms]	scale	n.a.
data_SAR	Yes	imp_ana_lv_thresh_01_04 ³⁴	Pacing threshold [V] at 0.4 ms	scale	n.a.
data_SAR	Yes	imp_ana_lv_thresh_01_05 ³⁵	Pacing threshold [V] at 0.5 ms	scale	n.a.
implantation_analyzer_data	No	imp_ana_lv_pns_amp_01	at pacing amplitude [V]	scale	n.a.
data_SAR	Yes	imp_ana_lv_pns_amp_01_04 ³⁶	Phrenic nerve stimulation threshold [V] at 0.4 ms	scale	n.a.
data_SAR	Yes	imp_ana_lv_pns_amp_01_05 ³⁷	Phrenic nerve stimulation threshold [V] at 0.5 ms	scale	n.a.

Pacing threshold measurements will be reported for 0.4 and 0.5 ms separately. See the justification above.

The above analyses are performed for the following 12 vector permutations, respectively:

- 01 LV1 tip to LV2 ring
- 02 LV1 tip to LV4 ring
- 03 LV1 tip to RV coil
- 04 LV1 tip to ICD
- 05 LV2 ring to LV1 tip
- 06 LV2 ring to LV4 ring
- 07 LV2 ring to RV coil
- 08 LV3 ring to LV2 ring
- 09 LV3 ring to LV4 ring
- 10 LV3 ring to RV coil
- 11 LV4 ring to LV2 ring
- 12 LV4 ring to RV coil

³⁴ IF imp_ana_lv_pulse_01 =0.4 THEN imp_ana_lv_thresh_01_04 = imp_ana_lv_thresh_01

³⁵ IF imp_ana_lv_pulse_01 =0.5 THEN imp_ana_lv_thresh_01_05 = imp_ana_lv_thresh_01

³⁶ IF imp_ana_lv_pulse_01 = 0.4 THEN imp_ana_lv_pns_amp_01_04 = imp_ana_lv_pns_amp_01

³⁷ IF imp_ana_lv_pulse_01 = 0.5 THEN imp_ana_lv_pns_amp_01_05 = imp_ana_lv_pns_amp_01

Implantation Analyzer Data / LV /12 Pacing Vectors / Not-measured

Data file, identifier_patient_display_id_full	Descriptive	Variable name	Variable label, NEW prefix added to all labels "Implantation analyzer data, [specification ... to ...]: "	Variable level	Nominal values
implantation_analyzer_data	No	imp_ana_lv_imp_01_no	-	nominal	Above range Below range Not done
data_SAR	Yes	imp_ana_lv_imp_01_no_SAR ³⁸	Implantation analyzer data, LV1 tip to LV2 ring: Pacing impedance	nominal	Out of range Measured
implantation_analyzer_data	Yes	imp_ana_lv_thresh_01_no	no capture with maximum output possible	nominal	True / False
implantation_analyzer_data	Yes	imp_ana_lv_pns_01	Phrenic nerve stimulation detected	nominal	Yes / No

The above analyzes are performed for all 12 vector permutations, respectively.

³⁸ IF imp_ana_lv_imp_01_no = Above range OR Below range THEN imp_ana_lv_imp_01_no_SAR = Out of range
ELSE IF imp_ana_lv_imp_01 ≠ missing THEN imp_ana_lv_imp_01_no_SAR = Measured

Implantation Device Data / RA

Data file, identifier patient_display_id_full	Descriptive	Variable name	Variable label, NEW prefix added to all labels "Implantation device data, RA:"	Variable level	Nominal values
implantation_device_data	Yes	imp_ra_amp	Sensing amplitude [mV]	metric	n.a.
implantation_device_data	Yes	imp_ra_imp	Pacing impedance [Ω]	scale	n.a.
implantation_device_data	Yes	imp_ra_thresh	Pacing threshold [V] at Pulse width 0.4 ms	scale	n.a.

The CIP requires using 0.4 ms pulse width for all RA and RV threshold measurements. However, in the SAP version 1.0 it has been defined that it will be tested during blind review whether a meaningful number of measurements were performed with another pulse duration than 0.4 ms. This test showed that very few or no threshold measurements used other values than 0.4 ms at RA and RV measurements.

Therefore, **thresholds of device measurements will be reported for 0.4 ms pulse duration** only and measurements at other pulse duration will be discarded.

Implantation Device Data / RA / Not-measured

Data file, identifier patient_display_id_full	Descriptive	Variable name	Variable label	Variable level	Nominal values
implantation_device_data	No	imp_ra_amp_no	-	nominal	Not measurable: P-wave visible but [...] Not measurable: No P-wave visible Not done
data_SAR	Yes	imp_ra_amp_no_SAR ³⁹	Implantation device data, RA: Sensing amplitude	nominal	Not measurable: P-wave visible but Measured
implantation_device_data	No	imp_ra_imp_no	-	nominal	Out of range >3000 Out of range <200 Not measurable: no overpacing possible Not done
data_SAR	Yes	imp_ra_imp_no_SAR ⁴⁰	Implantation device data, RA: Pacing impedance	nominal	Out of range Measured
implantation_device_data	No	imp_ra_thresh_no	-	nominal	Not measured at 0.4 ms No capture with 7.5V possible Not measurable: no overpacing possible Not done
data_SAR	Yes	imp_ra_thresh_no_SAR ⁴¹	Implantation device data, RA: Pacing threshold	nominal	No capture with 7.5V possible Measured

³⁹ IF imp_ra_amp_no = Not measurable: P-wave visible but ... THEN imp_ra_amp_no_SAR = imp_ra_amp_no
ELSE IF imp_ra_amp ≠ missing THEN imp_ra_amp_no_SAR = Measured

⁴⁰ IF imp_ra_imp_no = Out of range >3000 OR Out of range <200
THEN imp_ra_imp_no_SAR = Out of range
ELSE IF imp_ra_imp ≠ missing THEN imp_ra_imp_no_SAR = Measured

⁴¹ IF imp_ra_thresh_no = No capture ... THEN imp_ra_thresh_no_SAR = imp_ra_thresh_no
ELSE IF imp_ra_thresh ≠ missing THEN imp_ra_thresh_no_SAR = Measured

Implantation Device Data / RV

Data file, identifier patient_display_id_full	Descriptive	Variable name	Variable label, NEW prefix added to all labels "Implantation device data, RV: "	Variable level	Nominal values
implantation_device_data	Yes	imp_rv_amp	Sensing amplitude [mV]	scale	n.a.
implantation_device_data	Yes	imp_rv_imp	Pacing impedance [Ω]	scale	n.a.
implantation_device_data	Yes	imp_rv_thresh	Pacing threshold [V] at Pulse width 0.4 ms	scale	n.a.
implantation_device_data	Yes	imp_rv_shock	Painless shock impedance [Ω]	scale	n.a.

Measurements at other pulse widths than 0.4 ms will be discarded (see above).

Implantation Device Data / RV / Not-measured

Data file, identifier_patient_display_id_full	Descriptive	Variable name	Variable label	Variable level	Nominal values
implantation_device_data	No	imp_rv_amp_no	-	nominal	No intrinsic rhythm Amplitude visible but too low to measure During intrinsic rhythm no R-wave visible Not done
data_SAR	Yes	imp_rv_amp_no_SAR ⁴²	Implantation device data, RV: Sensing amplitude	nominal	Amplitude visible but too low to measure During intrinsic rhythm no R-wave visible Measured
implantation_device_data	No	imp_rv_imp_no	-	nominal	Out of range >3000 Out of range <200 Not measurable: no overpacing possible Not done
data_SAR	Yes	imp_rv_imp_no_SAR ⁴³	Implantation device data, RV: Pacing impedance	nominal	Out of range Measured
implantation_device_data	No	imp_rv_thresh_no	-	nominal	Not measured at 0.4 ms No capture with 7.5V possible Not measurable: no overpacing possible Not done
data_SAR	Yes	imp_rv_thresh_no_SAR ⁴⁴	Implantation device data, RV: Pacing threshold	nominal	No capture with 7.5V possible Measured
implantation_device_data	No	imp_rv_shock_no	-		Out of range >150 Out of range <25 Not done
data_SAR	Yes	imp_rv_shock_no_SAR ⁴⁵	Implantation device data, RV: Painless shock impedance	nominal	Out of range Measured

⁴² IF imp_rv_amp_no = Amplitude visible ... OR
imp_rv_amp_no = During intrinsic ... THEN imp_rv_amp_no_SAR = imp_rv_amp_no
ELSE IF imp_rv_amp ≠ missing THEN imp_rv_amp_no_SAR = Measured

⁴³ IF imp_rv_imp_no = Out of range >3000 OR
imp_rv_imp_no = Out of range <200 THEN imp_rv_imp_no_SAR = Out of range
ELSE IF imp_rv_imp ≠ missing THEN imp_rv_imp_no_SAR = Measured

⁴⁴ IF imp_rv_thresh_no = No capture ... THEN imp_rv_thresh_no_SAR = imp_rv_thresh_no
ELSE IF imp_rv_thresh ≠ missing THEN imp_rv_thresh_no_SAR = Measured

⁴⁵ IF imp_rv_shock_no = Out of range >150 OR
imp_rv_shock_no = Out of range <25 THEN imp_rv_shock_no_SAR = Out of range
ELSE IF imp_rv_shock ≠ missing THEN imp_rv_shock_no_SAR = Measured

Implantation Device Data / LV / 7 Sensing Vectors

Data file, identifier_patient_display_id_full	Descriptive	Variable name	Variable label, NEW prefix added to all labels "Implantation device data, [specification ... to ...]"	Variable level	Nominal values
implantation_device_data	Yes	imp_lv_amp_01	Sensing amplitude [mV]	scale	n.a.

The above analyses are performed for all 7 vector permutations, respectively:

- 01 LV1 tip to LV2 ring
- 02 LV1 tip to ICD
- 03 LV2 ring to LV3 ring
- 04 LV2 ring to ICD
- 05 LV3 ring to LV4 ring
- 06 LV3 ring to ICD
- 07 LV4 ring to ICD

Implantation Device Data / LV / 7 Sensing Vectors / Not-measured

Data file, identifier_patient_display_id_full	Descriptive	Variable name	Variable label	Variable level	Nominal values
implantation_device_data	No	imp_lv_svect_no	-	nominal	No intrinsic rhythm Amplitude visible but too low to measure During intrinsic rhythm no R-wave visible Not done
data_SAR	Yes	imp_lv_svect_SAR ⁴⁶	Implantation device data, any LV pacing vector: Sensing amplitude	nominal	Amplitude visible but too low to measure During intrinsic rhythm no R-wave visible At least one vector measured

⁴⁶ IF imp_lv_amp_no = Amplitude visible but too low to measure
 THEN imp_lv_svect_SAR = Amplitude visible but too low to measure
 ELSE IF imp_lv_amp_no = During intrinsic rhythm no R-wave visible
 THEN imp_lv_svect_SAR = During intrinsic rhythm no R-wave visible
 ELSE IF any j=1-7 imp_lv_amp_0j ≠ missing
 THEN imp_lv_svect_SAR = At least one vector measured

Implantation Device Data / LV / Programmed Pacing Vectors

Final programmed pacing vectors are handled in the multipole_pacing CRFs.

Data file, identifier_patient_display_id_full	Descriptive	Variable name	Variable label, NEW prefix added to all labels "Implantation device data, first LV pacing vector: "	Variable level	Nominal values
implantation_device_data	Yes	imp_lv_first_imp	Pacing impedance [Ω]	scale	n.a.
implantation_device_data	No	imp_lv_first_thresh	Pacing threshold [V]	scale	n.a.
implantation_device_data	No	imp_lv_first_pulse	at Pulse width [ms]	scale	n.a.
data_SAR	Yes	imp_lv_first_thresh_04 ⁴⁷	Pacing threshold [V] at Pulse width 0.4 ms	scale	n.a.

Data file, identifier_patient_display_id_full	Descriptive	Variable name	Variable label, NEW prefix added to all labels "Implantation device data, second LV pacing vector: "	Variable level	Nominal values
implantation_device_data	Yes	imp_lv_sec_imp	Pacing impedance [Ω]	scale	n.a.
implantation_device_data	No	imp_lv_sec_thresh	Pacing threshold [V]	scale	n.a.
implantation_device_data	No	imp_lv_sec_pulse	at Pulse width [ms]	scale	n.a.
data_SAR	Yes	imp_lv_sec_thresh_04 ⁴⁸	Pacing threshold [V] at Pulse width 0.4 ms	scale	n.a.

Data file, identifier_patient_display_id_full	Descriptive	Variable name	Variable label, NEW prefix added to all labels "Implantation device data, second LV pacing vector: "	Variable level	Nominal values
implantation_device_data	No	imp_lv_first_pvect	Programmed first LV pacing vector	nominal	[...]
implantation_device_data	No	imp_lv_sec_pvect	Programmed second LV pacing vector	nominal	[...]
data_SAR	Yes	imp_lv_first_sec_pvect_SAR ⁴⁹	Programmed first and second LV pacing vector	nominal	#

There are 132 possible vector combinations. All vector combinations used in the study have to be reported in the SAR, whereby the most frequent vector combination has to be reported in the CIR, only.

The CIP suggests using 0.4 ms pulse width for all LV threshold measurements, but other values were permitted. In the SAP version 1.0 it has been defined that it will be tested during blind review whether a meaningful number of measurements were performed with another pulse duration than 0.4 ms.

This test showed that very few or no LV threshold measurements used other values than 0.4 ms at implantation.

Therefore, **thresholds of device measurements will be reported for 0.4 ms pulse duration** only and measurements at other pulse duration will be discarded.

⁴⁷ IF imp_lv_first_pulse = 0.4, THEN imp_lv_first_thresh_04 = imp_lv_first_thresh

⁴⁸ IF imp_lv_sec_pulse = 0.4, THEN imp_lv_sec_thresh_04 = imp_lv_sec_thresh

⁴⁹ imp_lv_first_sec_pvect_SAR = combination of imp_lv_first_pvect and imp_lv_sec_pvect per patient

Implantation Device Data / LV / Programmed Pacing Vectors / Not-measured

Data file, identifier_patient_display_id_full	Descriptive	Variable name	Variable label	Variable level	Nominal values
implantation_device_data	No	imp_lv_first_imp_no	-	nominal	Out of range >3000 Out of range <200 Not measurable: no overpacing possible Not done
data_SAR	Yes	imp_lv_first_imp_no_SAR ⁵⁰	Implantation device data, first LV pacing vector: Pacing impedance	nominal	Out of range Measured
implantation_device_data	No	imp_lv_first_thresh_no	-	nominal	No capture with 7.5V possible Not measurable: no overpacing possible Not done
data_SAR	Yes	imp_lv_first_thresh_no_SAR ⁵¹	Implantation device data, first LV pacing vector: Pacing threshold	nominal	No capture with 7.5V possible Measured

Data file, identifier_patient_display_id_full	Descriptive	Variable name	Variable label	Variable level	Nominal values
implantation_device_data	No	imp_lv_sec_imp_no	-	nominal	Out of range >3000 Out of range <200 Not measurable: no overpacing possible Not done
data_SAR	Yes	imp_lv_sec_imp_no_SAR ⁵²	Implantation device data, second LV pacing vector: Pacing impedance	nominal	Out of range Measured
implantation_device_data	No	imp_lv_sec_thresh_no	-	nominal	No capture with 7.5V possible Not measurable: no overpacing possible Not done
data_SAR	Yes	imp_lv_sec_thresh_no_SAR ⁵³	Implantation device data, second LV pacing vector: Pacing threshold	nominal	No capture with 7.5V possible Measured

⁵⁰ IF imp_lv_first_imp_no = Out of range >3000 OR
imp_lv_first_imp_no = Out of range <200 THEN imp_lv_first_imp_no_SAR = Out of range
ELSE IF imp_lv_first_imp ≠ missing THEN imp_lv_first_imp_no_SAR = Measured

⁵¹ IF imp_lv_first_thresh_no = No capture ... THEN imp_lv_first_thresh_no_SAR = imp_lv_first_thresh_no
ELSE IF imp_lv_first_thresh ≠ missing THEN imp_lv_first_thresh_no_SAR = Measured

⁵² IF imp_lv_sec_imp_no = Out of range >3000 OR
imp_lv_sec_imp_no = Out of range <200 THEN imp_lv_sec_imp_no_SAR = Out of range
ELSE IF imp_lv_sec_imp ≠ missing THEN imp_lv_sec_imp_no_SAR = Measured

⁵³ IF imp_lv_sec_thresh_no = No capture ... THEN imp_lv_sec_thresh_no_SAR = imp_lv_first_thresh_no
ELSE IF imp_lv_sec_thresh ≠ missing THEN imp_lv_sec_thresh_no_SAR = Measured

Implantation Device Data / LV / Programmed Delay

Data file, identifier_patient_display_id_full	Descriptive	Variable name	Variable label, NEW prefix added to all labels "Implantation device data: "	Variable level	Nominal values
implantation_device_data	No	imp_order_rvlv	Pacing order	nominal	RV first LV first
implantation_device_data	Yes, for the above groups "RV first" and "LV first"	imp_lvlv_delay	LV-LV delay [ms]	scale	n.a.
implantation_device_data	Yes, for the above groups "RV first" and "LV first"	imp_rvlv_delay	RV-LV delay [ms]	scale	n.a.

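### The analyzer threshold status counts only 0.4 ms readings as Measured, so patients read only at 0.5 ms appear to drop out of the table

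*SAP*

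**What the plan says.** SAP 10.2 lists the analyzer measurements at implantation.

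- **0.4 ms values.** For the right atrium (RA) and right ventricle (RV), the main threshold variables `imp_ana_ra_thresh` and `imp_ana_rv_thresh` carry the label "Pacing threshold [V] at Pulse width 0.4 ms".
- **Other pulse widths.** These go into a second threshold field with its own pulse-width field. Values at 0.5 ms are copied from there by footnote 25 for RA, "IF imp_ana_ra_pulse =0.5 THEN imp_ana_ra_thresh_05 = imp_ana_ra_thresh2", and footnote 29 for RV, "IF imp_ana_rv_pulse =0.5 THEN imp_ana_rv_thresh_05 = imp_ana_rv_thresh2".
- **Why 0.5 ms is reported.** The blind review found that "in a meaningful number of threshold measurements, 0.5 ms has been used, but only single or no other values". The SAP therefore reports analyzer thresholds at both widths and discards any others.
- **Status variable.** The raw reason field has separate options for a threshold not taken at 0.4 ms and for failure to capture; they stand next to each other in the list as "Not measured at 0.4 ms No capture with maximum output". Footnote 28 (RA) and footnote 32 (RV) first pick out the no-capture code. Otherwise they apply "ELSE IF imp_ana_ra_thresh ≠ missing THEN imp_ana_ra_thresh_no_SAR = Measured" and "ELSE IF imp_ana_rv_thresh ≠ missing THEN imp_ana_rv_thresh_no_SAR = Measured" respectively.
- **Denominator.** SAP 5.1 bases relative frequencies of nominal variables on non-missing data.
- **Plexa.** SAP 19.2 reuses the chapter 10.2 definitions for the Plexa analysis set: RV for all leads, RA only for the DX lead.

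**The concern.** The decision to report 0.5 ms readings was carried into the threshold variables but not into the status variable beside them. The status label names the analyzer pacing threshold without restricting it to 0.4 ms, so a reader will take Measured to mean that a threshold was obtained. Under footnotes 28 and 32 it means only that a 0.4 ms threshold was obtained.

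The loss is one-sided. The no-capture branch does not look at pulse width, so every no-capture patient stays in the table, while patients with a successful 0.5 ms reading do not. If there is any no-capture at all, its percentage can only be pushed upward. At stake is the accuracy of two descriptive status tables at implantation, one of which (RV) describes the investigational Plexa lead.

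**Working it through.** The plan gives no figure for this status variable, so there is nothing of its own to reproduce. The check traces the rules and then applies the SAP's denominator.

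**Step 1: the denominator rule.** The first dummy table in SAP 5.1 confirms how percentages are formed. With 9 non-missing values, 5/9 = 55.6%; with 8 non-missing values, 4/8 = 50.0%. Missing values are left out of the denominator.

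**Step 2: trace of three kinds of patient (RA; RV is identical in structure).**

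| Patient | Raw reason code | 0.4 ms variable | 0.5 ms variable | Status under footnote 28 |
|---|---|---|---|---|
| Measured at 0.4 ms | none | filled | empty | Measured |
| Measured only at 0.5 ms | not measured at 0.4 ms | empty | filled | missing (neither branch applies) |
| No capture | no capture | empty | empty | No capture |

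The second row rests on an inference: that the 0.4 ms field is left empty when the reading was taken at 0.5 ms. The case report form is not shown. The inference comes from the field's label, the separate fields for other widths, and the dedicated reason code.

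**Step 3: formula.** Let x be the number with no capture, n04 the number measured at 0.4 ms and n05 the number measured only at 0.5 ms.

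- As written: x/(x + n04)
- With both widths counted: x/(x + n04 + n05)
- Ratio: (x + n04 + n05)/(x + n04)

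If x = 0, both percentages are 0. The only error is then that Measured shows n04 instead of n04 + n05.

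**Step 4: illustration.** The totals are the minimum analysis-set sizes in SAP chapter 4: 94 (Ilivia) and 166 (Plexa). Two inputs are assumed because the documents do not give them: x = 2, and a 0.5 ms share of 10%, 30% or 50% of the measured thresholds. For simplicity every patient is taken to have either a threshold or a no-capture code. Measured patients then number 94 − 2 = 92 and 166 − 2 = 164.

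| N | Assumed 0.5 ms share | n05 | As written | Both widths counted |
|---|---|---|---|---|
| 94 | 10% | 9 | 2/85 = 2.35% | 2/94 = 2.13% |
| 94 | 30% | 28 | 2/66 = 3.03% | 2/94 = 2.13% |
| 94 | 50% | 46 | 2/48 = 4.17% | 2/94 = 2.13% |
| 166 | 10% | 16 | 2/150 = 1.33% | 2/166 = 1.20% |
| 166 | 30% | 49 | 2/117 = 1.71% | 2/166 = 1.20% |
| 166 | 50% | 82 | 2/84 = 2.38% | 2/166 = 1.20% |

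The ratio is about 1.1, 1.4 and 2.0 at the three shares.

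**Step 5: where it does and does not apply.** Left-ventricular analyzer data are not affected, because no capture is reported there directly as true or false for each vector. RA and RV thresholds measured through the device are not affected either, because the SAP reports those at 0.4 ms only.

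**The case against.** The strongest reply is that the consequence is small and visible. Chapters 10 and 19 of the SAP contain no hypotheses. The Plexa pacing endpoint in SAP chapter 25 uses the investigator's assessment at three months, not the analyzer status. For analyzer data, protocol 8.4.1 and 8.4.2 ask for mean values, and those are computed from the 0.4 ms and 0.5 ms threshold variables, which are correct. SAP 5.1 provides for missing and non-missing counts, and the 0.5 ms row carries its own count, so a careful reader could rebuild the denominator. All of this stands, and it keeps the point minor. It does not make the rule right: the reader should not have to rebuild a count that the SAP can define correctly.

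Three stronger readings are tempting and go too far.

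- **That the implant no-capture rate is overstated as a matter of fact.** This needs at least one no-capture patient, and the documents report no such count. It also needs the 0.4 ms field to be empty for patients read at 0.5 ms, which is well supported but inferred.
- **That the status table contradicts the threshold tables.** Measured is tied to the 0.4 ms variable and is consistent with that row. Relative to the 0.5 ms row it is incomplete, not contradictory.
- **That the results for the investigational lead are affected throughout.** For Plexa, RA data are reported only for the DX lead, and the protocol's description of the DX functionality excludes atrial pacing. In practice only the RV status table matters there.

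**Conclusion.** The rule is wrong as written, with minor consequence. Footnotes 28 and 32 define Measured from the 0.4 ms variable alone, while the same section reports 0.5 ms thresholds because "in a meaningful number of threshold measurements, 0.5 ms has been used". Patients read only at 0.5 ms appear to receive a missing status, so the Measured count is too low by n05. Any no-capture percentage is too high by the factor (x + n04 + n05)/(x + n04); with no no-capture patients, only the counts are wrong.

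The actual size cannot be computed, since neither the no-capture count nor the 0.5 ms count is given. The factors of about 1.1 to 2.0 above rest on assumed shares of 10% to 50%. The conclusion also rests on the inferred empty 0.4 ms field. A reader might infer that a safety or pacing endpoint is touched. The documents do not support that, because no primary or secondary endpoint, significance level or sample size uses these variables.

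**What to change.** In footnote 28, change the second branch to: `ELSE IF imp_ana_ra_thresh ≠ missing OR imp_ana_ra_thresh_05 ≠ missing THEN imp_ana_ra_thresh_no_SAR = Measured`. In footnote 32, make the same change with `imp_ana_rv_thresh`, `imp_ana_rv_thresh_05` and `imp_ana_rv_thresh_no_SAR`. SAP 19.2 takes over the correction by its reference to chapter 10.2.

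The cost is one condition in each of two footnotes and the matching line of code. No new data are needed. If some patients turn out to have both fields filled, the added condition does no harm.
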